5.2 Secondary Efficacy Endpoints

5.2.1 Key Secondary Endpoints

The key secondary endpoints are:

- The change from baseline (CBL) to Week 78 in A-IADL-W
- The change from baseline (CBL) to Week 78 in CDR-SB

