8.1.5 Multiplicity of Secondary Endpoints

The graphical approach will be used on testing multiple endpoints in a predefined order to strongly control the family-wise type 1 errors arising from multiple comparisons (Bretz 2009). The alpha recycle is described in detail in Figure 2. For the primary efficacy endpoint (CFBL to week 78 in ADAS-Cog 13, i.e., H1) hypothesis testing, the initial 2-sided significance level is set to 0.05. Only if the H1 testing is successful will the next two key secondary endpoints: CFBL to week 78 in A-IADL (H2) and CFBL to week 78 in CDR-SB (H3), be tested each at an alpha level of 0.025. If H2 shows significance, its alpha level of 0.025 is passed on to H3 for testing at an endpoint-specific alpha level of 0.025+0.025=0.05. However, if H2 is not significant, H3 is still tested at the reserved alpha level of 0.025. In this scenario, if H3 turns out to be significant, the alpha level for H2 is recycled back for re-testing at 0.05.

Since a graphical approach is used in the analysis, the overall type I error rate is strongly controlled at the 2-sided α =0.05. The hypothesis testing for the additional clinical endpoints (not presented in Figure 2) will be done without control for type I errors due to multiple comparisons and the p-values will be considered nominal.

8.2 Visit Windows and Efficacy Data Algorithms and Definitions/Handling of Dropouts or Missing Data

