A-IADL-IRT has a score range of 20-80 and will be calculated and transferred from a third party vendor for categorical responder analysis (Dubbelman 2022a). A-IADL-W has a score range of 0-100 and is calculated as follows: (sum of all scores / number of questions scored) × 25 which will be used for secondary efficacy analysis (Table 10, Teng 2023). For A-IADL-IRT, higher scores indicates better functioning, while for A-IADL-W, higher scores indicates worse functioning or more impairment.

If <25% (11 or fewer of 47; or 17 or fewer of 70 questions are answered) are answered as "don't know", A-IADL-W will be derived without imputation and considered valid. If the scores from more than 11 items are not available, A-IADL-W at that visit will be considered missing.

Table 10 A-IADL Algorithm for derivation of Total Score

Algorithm

If Yes is selected in main question with performance level:

No = 0

Yes, slightly more difficult = 1

Yes, more difficult =2

Yes, much more difficult =3

Yes, he/she is no longer able to perform this task =4

If No is selected in main question with performance level:

He/she was no longer able to do so due to cognitive problems = 4

He/she was no longer able to do so due to physical problems = Not scored

He/she has never done that before = Not scored

Other, please state = Not scored

A-IADL-W = (sum of all scores / number of questions scored) \times 25

CDR-SB: The CDR consists of 6 boxes for a score range of 0-18 (Table 11). It is a global rating scale used to assess the stage and severity of dementia (Morris 1993). It uses a structured, clinician-rated interview that collects information on cognitive and functional capacity from both the subject and caregiver. Higher score on CDR-SB indicates more advanced AD.

The CDR-SB will be determined by adding the individual scores from each of the six domains. The same imputation technique will be applied to missing CDR-SB boxes or sub-items. If only 1 of 6 boxes (<25%) of the CDR is missing, the sum of the boxes will be imputed by prorating the sum from the other 5 boxes: CDR-SB Total Score = Total score from the completed items × [maximum total score (=18) / maximum total score corresponding to the 5 completed boxes (=15)]. The imputed number will be derived and rounded up to the nearest integer. If more than 1 box is missing, the total score of CDR-SB at that visit will be considered missing.

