CDR-G: The CDR scale also provides a derived global score (CDR-G) which indicates disease stage, with CDR-G= 0 indicating no impairment, CDR-G= 0.5 indicating MCI, CDR-G=1

indicating Mild AD, and CDR-G = 2 or 3 indicating Moderate and Severe AD, respectively. CDR-G scale will be used for categorical responder analyses. In the event of a single missing box score on the CDR-SB, the aforementioned imputed CDR-SB score can be used to derive CDR-G score.

Table 11 CDR Items and Algorithm for derivation of Item Scores and Total Score

Item	Algorithm	Range
Memory	0=normal, 0.5=questionable; 1=mild, 2=moderate, 3=severe	0-3
Orientation	0=normal, 0.5=questionable; 1=mild, 2=moderate, 3=severe	0-3
Judgment and Problem Solving	0=normal, 0.5=questionable; 1=mild, 2=moderate, 3=severe	0-3
Community Affairs	0=normal, 0.5=questionable; 1=mild, 2=moderate, 3=severe	0-3
Home and Hobbies	0=normal, 0.5=questionable; 1=mild, 2=moderate, 3=severe	0-3
Personal Care	0=normal/questionable, 1=mild, 2=moderate, 3=severe	0-3
CDR-SB Total	Sum of all items	0-18

MMSE: The MMSE is a measure of global cognition that is widely used for clinical staging of AD (Folstein 1975). It consists of 11 domains items for a score range of 0-30 to assess general cognitive function (Table 12). Higher score on MMSE means better cognitive skills.

The same imputation algorithm will be applied to the MMSE. If 2 or fewer of 11 domains (<25%) of the MMSE are missing, the total score will be imputed by prorating the sum from the other completed domains: MMSE Total Score = Total score from the completed domains × [maximum total score (=30) / maximum total score corresponding to the completed domains]. The imputed number will be derived and rounded up to the nearest integer. If the scores from more than 2 domains are not available, the MMSE at that visit will be considered missing. For MMSE, higher total scores indicate better cognition.

Table 12 MMSE Domains and Algorithm for derivation of Domain Scores and Total Score

Domain	Algorithm	Range
Orientation to Time	5 questions: Total number of "Correct" answers	0-5
Orientation to Place	5 questions: Total number of "Correct" answers	0-5
Registration	3 words: Total number of "Correct" answers	0-3
Calculation	5 questions: Total number of "Correct" answers	0-5
Recall	3 words: Total number of "Correct" answers	0-3
Naming	2 questions: Total number of "Correct" answers	0-2
Repetition	1 question: Total number of "Correct" answer	0-1

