NPI-12: Early AD patients may experience various neuropsychiatric symptoms that emerge and worsen with disease progression and contribute to the morbidity and healthcare burden of AD (Forester 2019). The NPI assesses the neuropsychiatric or behavioral symptoms of AD, including their frequency and severity (Cummings 1997). It is a self-administered questionnaire completed by caregivers about subjects for whom they care. The NPI-12 has 12 sub-items, each item has score range of 0-12 with a NPI-total score range of 0-144 for subject's symptoms and 0-60 for caregiver distress (Table 14). Higher scores on each NPI sub-item indicate more severe or frequent occurrence of that symptom. Higher scores on NPI-12 indicate more severe burden of neuropsychiatric or behavioral symptoms.

The same imputation algorithm will be applied to the NPI-12 and Caregiver Distress. If 2 or fewer of 12 items (<25%) of the NPI-12 are missing, the total score will be imputed by prorating the sum from the other completed items: Total score = total score from the completed items × [maximum total score (=144) / maximum total score corresponding to the completed items]. If 2 or fewer of 12 items (<25%) of the Caregiver Distress are missing, the total Caregiver Distress score will be and derived and imputed by prorating the sum from the other completed items: Total Caregiver Distress score = total score from the completed items × [maximum total score (=60) / maximum total score corresponding to the completed items].

The imputed number will be rounded up to the nearest integer. If the scores from more than 2 items are not available, the NPI-12 at that visit will be considered missing.

Table 14 NPI-12 Items and Algorithm for derivation of Item Scores and Total Score

Item	Algorithm	Range	Caregiver Distress Range
Delusions	Frequency (0-4), Severity (0-3)	0-12	0-5
Hallucinations	Frequency (0-4), Severity (0-3)	0-12	0-5
Agitation/Aggression	Frequency (0-4), Severity (0-3)	0-12	0-5
Depression/Dysphoria	Frequency (0-4), Severity (0-3)	0-12	0-5
Anxiety	Frequency (0-4), Severity (0-3)	0-12	0-5
Elation/Euphoria	Frequency (0-4), Severity (0-3)	0-12	0-5
Apathy/Indifference	Frequency (0-4), Severity (0-3)	0-12	0-5
Disinhibition	Frequency (0-4), Severity (0-3)	0-12	0-5
Irritability/Lability	Frequency (0-4), Severity (0-3)	0-12	0-5
Aberrant Motor Behavior	Frequency (0-4), Severity (0-3)	0-12	0-5
Sleep	Frequency (0-4), Severity (0-3)	0-12	0-5

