8.3.5 Responder Analyses

Additional efficacy analyses may include responder analysis based on the efficacy outcomes. Since mean changes from baseline may be affected by outliers, responder analyses provide insights into drug effects that are less affected by outlier values. The following responder or categorical analyses may be conducted to complement the CBL analyses of the main efficacy outcomes including the ADAS-Cog 13, A-IADL, and CDR-SB. They may also be conducted on the MMSE and CDR-G which are part of the study inclusion criteria. Subjects with missing scores at the visits will be excluded from the responder analyses for that variable/visit. The responder categories are defined as follows:

Primary cognitive outcome, ADAS-Cog 13 (Mohs 1997):

- Number and percentage of subjects whose scores remain stable or improve from baseline (lower scores = less deficits): CBL ≤ 0 at Week 78
- Number and percentage of subjects whose scores worsen from baseline by less than:
 - o ADAS-Cog 13 CBL \leq 3.5 points at Week 78

o ADAS-Cog 13 CBL ≤ 1.5 points at Week 78

Key secondary outcome, A-IADL-IRT scores for functional categories (Dubbelman 2022a):

- Number and percentage of subjects whose A-IADL-IRT scores at Week 78 remain within the same category as baseline or improve to next higher category (higher scores = less impairment), based on the following 3 functional categories:
 - Category of "No-Mild" deficits with IRT scores \geq 50
 - Category of "Moderate" deficits with IRT scores = 40-49 inclusive
 - o Category of "Severe" deficits with IRT scores < 40

Key secondary outcomes, CDR-SB for functional categories (O'Bryant 2008):

- Number and percentage of subjects whose CDR-SB values at Week 78 remain within the same category as baseline or improve to less advanced category (lower scores = lower disease severity), based on the following 3 categories or disease stages:
 - o MCI or no impairment defined as CDR-SB from 0-4.0 inclusive
 - Mild AD defined as CDR-SB from 4.5 9.0 inclusive
 - Moderate AD defined as CDR-SB from 9.5 15.5 inclusive

Stage of AD based on CDR-G for disease stages (Morris 1993):

- Number and percentage of subjects whose CDR-G values at Week 78 remain within the same category as baseline or improve (lower scores = less severe category), based on the following 3 categories:
 - o MCI or no mpairment defined as CDR-G ≤ 0.5
 - Mild AD defined as CDR-G > 0.5 and ≤ 1.0
 - Moderate AD defined as CDR-G > 1 and \leq 2.0

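### SAP 8.2.4 rounds a prorated CDR-SB up to a whole integer on a half-point scale; the rule should be nearest 0.5 (minor correction, no threat to the H3 test)

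*SAP*

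**What the plan says.** SAP 5.2.1 lists as a key secondary endpoint: "The change from baseline (CBL) to Week 78 in CDR-SB". SAP 8.1.5 makes it H3; once the primary succeeds, the two key secondaries are to "be tested each at an alpha level of 0.025", with alpha recycling.

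Proration is set out in SAP 8.2.4. The condition is "If only 1 of 6 boxes (<25%) of the CDR is missing". The sum of the five completed boxes is multiplied by 18 and divided by 15, and then: "The imputed number will be derived and rounded up to the nearest integer". With two or more boxes missing, the total is missing.

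SAP Table 11 scores five boxes at 0, 0.5, 1, 2 or 3 and Personal Care at 0, 1, 2 or 3. Protocol 7.1.11.4 gives the levels 0, 0.5, 1, 2 and 3 for every box. The stage bands in SAP 8.3.5 are also in half points: "MCI or no impairment defined as CDR-SB from 0-4.0 inclusive", then Mild AD from 4.5 to 9.0 and Moderate AD from 9.5 to 15.5. SAP 8.3.6.1 uses the same cuts for time to progression.

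In the same section, the MMSE and QoL-AD rules also round up to a whole number, and for NPI-12 "The imputed number will be rounded up to the nearest integer". Prorated ADAS-Cog totals are rounded up too, but to two decimals. For the global score with one box missing, the SAP says that "the aforementioned imputed CDR-SB score can be used to derive CDR-G score".

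**The concern.** A whole-number rule discards half points that the scale and the cuts rely on, and rounding always upward makes the error one-directional. Higher CDR-SB is worse, so each affected record looks more impaired than its five observed boxes imply. SAP 8.2.3 does not impute missing baselines, so the error falls mainly on post-baseline scores and enters the change score as apparent worsening.

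A small shift matters most at a stage cut, where it changes a category and hence a responder or progression outcome. The direction also differs by scale. Rounding up goes against the subject on CDR-SB and NPI-12 but favours the subject on MMSE and QoL-AD, so no single conservative rationale explains it.

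**Working it through.** **Inputs.** Maximum per box 3, six boxes, box levels from Table 11, proration and rounding from SAP 8.2.4, cuts from SAP 8.3.5 and 8.3.6.1. The share p of CDR records with exactly one missing box is not in the documents; I assume 0.5% to 10%.

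**The plan's own figures.** 6 × 3 = 18 and 5 × 3 = 15, so the factor is 18/15 = 1.2. One box of six is 16.7%, below 25%. Both agree with the SAP. Listing all box combinations gives attainable totals of 0, 0.5, 1, 1.5 and so on up to 16, then 17 and 18, so half-point totals are ordinary values.

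**Effect on one affected record.** For a five-box sum S, compare 1.2 × S with its rounded value:

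| S | 1.2 × S | Rounded up | Nearest integer | Nearest 0.5 |
|---|---|---|---|---|
| 0.5 | 0.6 | 1 | 1 | 0.5 |
| 1.0 | 1.2 | 2 | 1 | 1.0 |
| 1.5 | 1.8 | 2 | 2 | 2.0 |
| 2.0 | 2.4 | 3 | 2 | 2.5 |
| 2.5 | 3.0 | 3 | 3 | 3.0 |
| 3.0 | 3.6 | 4 | 4 | 3.5 |
| 3.5 | 4.2 | 5 | 4 | 4.0 |
| 4.0 | 4.8 | 5 | 5 | 5.0 |

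The errors repeat every 2.5 points of S. Over S = 0.5 to 9 (18 values, equally weighted):

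- Rounded up: errors cycle +0.4, +0.8, +0.2, +0.6, 0. Three cycles plus three values give (3 × 2.0 + 1.4)/18 = 7.4/18 = +0.41; maximum +0.8. Fifteen values rise, three (2.5, 5, 7.5) are unchanged, none falls.
- Nearest integer: errors cycle +0.4, −0.2, +0.2, −0.4, 0. Mean 0.4/18 = +0.02; range −0.4 to +0.4.
- Nearest 0.5: errors cycle −0.1, −0.2, +0.2, +0.1, 0. Mean −0.1/18 = −0.006; range −0.2 to +0.2.

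Stopping at S = 8 gives +0.40, +0.03 and −0.01.

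**Implied missing box.** S = 1 becomes 2, so the missing box is set to 1 although the observed boxes average 0.2. S = 3.5 becomes 5, an implied box of 1.5, which is not a level in Table 11.

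**Stage cuts.** Of all five-box sums from 0 to 15, only S = 3.5 lands in a different category at 4.0/4.5 or 9.0/9.5 under rounding up than under nearest 0.5: 5 (Mild AD) against 4.0 (MCI). At the top of the Moderate band, S = 13 becomes 16 rather than 15.5, but SAP 8.3.6.1 treats Moderate or worse as one category, so no progression event depends on it.

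**Effect on an arm mean.** Shift ≈ p × 0.4:

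| p (assumed) | Shift in arm mean |
|---|---|
| 0.5% | 0.002 |
| 1% | 0.004 |
| 2% | 0.008 |
| 5% | 0.02 |
| 10% | 0.04 |

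**Effect on the treatment difference.** Shift ≈ (p active − p placebo) × 0.4. This is zero in expectation when p and the scores among affected records match across arms. Even 10% in one arm and none in the other gives 0.10 × 0.4 = 0.04.

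**Other scales.** The size depends on what is missing. For MMSE with a five-point domain missing, the factor is 30/25 = 1.2 and the errors cycle 0.8, 0.6, 0.4, 0.2, 0 (mean 0.4). With a one-point domain missing and 20 to 29 points on the rest, the mean is (9 + 8 + … + 0)/(29 × 10) = 45/290 = 0.16. There is no single MMSE figure.

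**The case against.** A reader might infer that the rule biases the key secondary test, and might set 0.4 points against the 1.25-point CDR-SB effect in Protocol 2.3.1.1. The documents support neither. The test is of a between-arm difference and the rule is identical in both arms; nothing in the plan suggests that single-box missingness would differ by treatment. The 0.4 is a shift per affected record, whereas 1.25 is a difference between group means, so the comparable quantity is p × 0.4. That objection stands in full.

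The wording may be loose. Rounding up and rounding to the nearest are different conventions, and the ADAS-Cog rule mixes them in the same way. If ordinary rounding was meant, the mean error falls to +0.02 to +0.03 and S = 3.5 becomes 4. Half points are still lost, with errors up to 0.4 either way, and the text still needs clarifying.

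Nor is the progression event at S = 3.5 necessarily false: if the missing box was really 1, the true total is 4.5, which is Mild AD. The point is that rounding, and not the observed boxes, decides the category. The responder and time-to-event analyses are optional, and SAP 8.1.5 makes their p-values nominal.

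For CDR-G, one can argue that a conversion is implied, because SAP 8.2.4 and 8.3.5 attach the same stage names to CDR-G values and CDR-SB bands. That is fair, but nowhere is it stated as the conversion, and the permission to use the prorated sum is only optional. Finally, MMSE, NPI-12 and QoL-AD are integer-scored, so the half-point argument does not apply to them; only the upward direction does.

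**Conclusion.** The rule as written is wrong for a half-point scale. Taken literally, it raises each affected CDR-SB by about 0.4 points on average (maximum 0.8), never lowers one, and moves one five-box sum, 3.5, across the MCI to Mild AD cut. The average rests on equal weighting of sums from 0.5 to 9 and on the literal reading of rounding up.

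The effect on results is small: about 0.002 to 0.04 points on an arm mean for an assumed 0.5% to 10% of records with one missing box, and none in expectation on the treatment difference if affected records are alike in the two arms. This is a minor specification error and not a threat to the H3 test. The CDR-G derivation from a prorated sum is undefined, but it touches only nominal analyses.

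**What to change.** - **CDR-SB:** round a prorated total to the nearest 0.5. This fits the scale and the cuts and removes the systematic shift. Leaving the total unrounded is not a clean alternative for staging, because 4.2 falls in neither the 0 to 4.0 band nor the 4.5 to 9.0 band.
- **MMSE, NPI-12 and QoL-AD:** replace rounding up with rounding to the nearest integer.
- **CDR-G with one box missing:** either derive it from the corrected CDR-SB by a stated conversion, for example the SAP 8.3.5 stage bands, or set it to missing.

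The cost is about one sentence per scale, with no effect on design or power. Setting CDR-G to missing drops those records from the CDR-G analyses; a stated conversion keeps them but rests on the prorated sum.

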5.2.2 Additional Secondary Efficacy Endpoints

The additional secondary efficacy endpoints are:

- The CBL to Week 78 in ADAS-Cog 11
- The CBL to Week 78 in DAD
- The CBL to Week 78 in NPI
- The CBL to Week 78 in MMSE
- The CBL to Week 78 in QoL-AD
- The CBL to Week 78 in RUD Lite
- The CBL to Weeks 13, 26, and 52 in ADAS-Cog 13 and ADAS-Cog 11 scores
- The CBL to Weeks 26 and 52 in A-IADL-W, CDR-SB, DAD, and NPI scores
- The CBL to Weeks 13, 26, 39, 52, and 65 in MMSE scores

The CBL to Week 52 in QoL-AD (subject and informant) and RUD Lite scores

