Appetite Disorder	Frequency (0-4), Severity (0-3)	0-12	0-5
NPI-12 Total	Sum of all items	0-144	0-60

QoL-AD: The QoL-AD consists of 13 items for a score range of 13-52 for participant (subject) and informant (cargiver or study partner) (Logsdon 2002, Table 15), where higher scores indicate better quality of life.

The same imputation algorithm will be applied to the QoL-AD participant and informant. If 3 or fewer of 13 items (<25%) of the QoL-AD are missing, the total score will be imputed by prorating the sum from the other completed items: Total score = total score from the completed items × [maximum # of items (=13) / (# of completed items)]. The imputed number will be rounded up to the nearest integer. If the scores from more than 3 items are not available, the QoL-AD at that visit will be considered missing.

Table 15 QoL-AD (Participant and Informant) Items and Algorithm for derivation of Item Scores and Total Score

Item	Algorithm	Range
Physical Health	Poor (1), Fair (2), Good (3), Excellent (4)	1-4
Energy	Poor (1), Fair (2), Good (3), Excellent (4)	1-4
Mood	Poor (1), Fair (2), Good (3), Excellent (4)	1-4
Living Situation	Poor (1), Fair (2), Good (3), Excellent (4)	1-4
Memory	Poor (1), Fair (2), Good (3), Excellent (4)	1-4
Family	Poor (1), Fair (2), Good (3), Excellent (4)	1-4
Marriage	Poor (1), Fair (2), Good (3), Excellent (4)	1-4
Friends	Poor (1), Fair (2), Good (3), Excellent (4)	1-4
Self as a Whole	Poor (1), Fair (2), Good (3), Excellent (4)	1-4
Ability to Do Chores Around the House	Poor (1), Fair (2), Good (3), Excellent (4)	1-4
Ability to Do Things for Fun	Poor (1), Fair (2), Good (3), Excellent (4)	1-4
Money	Poor (1), Fair (2), Good (3), Excellent (4)	1-4
Life as a Whole	Poor (1), Fair (2), Good (3), Excellent (4)	1-4
QoL Total	Sum of all items	13-52

RUD Lite: The RUD Lite consists of two sections related to the caregiver and to the subject (Wimo 2013). In particular, the following reported hours/minutes or reported events will be listed and summarized by treatment and by baseline MMSE using descriptive statistics. Missing data will be left blank without imputation.

- Caregiver sleep time (hours and minutes) in the last 30 days
- Caregiver time (hours and minutes) and number of days in the last 30 days in assisting subject with tasks in toilet visits, eating, dressing, grooming, walking and bathing

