- Caregiver time (hours and minutes) and number of days in the last 30 days in assisting subject with tasks in shopping, food preparation, housekeeping, laundry, transporation, taking medication, and managing financial matters
- Caregiver time (hours and minutes) and number of days in the last 30 days in supervising the subject to prevent dangerous events
- Number of times the subject is admitted in a hospital (for more than 24 hours) since last visit
- Number of times the subject is admitted in a hospital emergency room (for less than 24 hours) since last visit

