8.3.3 Analyses of Key Secondary and Other Secondary Endpoints

The same MMRM method applied to the primary efficacy endpoint will be used to evaluate the between-treatment difference for the key secondary endpoints and the other secondary endpoints using the FAS. The same treatment policy strategy as that applied to the primary efficacy endpoint will be used for the secondary efficacy endpoints analysis. Differences between the two treatment groups, the p-values, and the 2-sided 95% CIs will be calculated within the framework of MMRM. The model will include all terms as in the primary endpoint model except that the baseline values will be corresponding to the baseline value for each parameter. Note that only the post-baseline visits on which the endpoints are scheduled to be measured will be included in the model.

The main analysis population is the FAS. Similar sensitivity analyses as for primary endpoint will be repeated for the key secondary and other secondary endpoints. As supportive analysis, the key and other secondary endpoints will also be analyzed using the PPP, and CP. Additional sensitivity analyses using MMRM with Last Observation Carried Forward (LOCF) may be performed.

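### RUD Lite: SAP 5.2.2 and 8.3.3 conflict with 8.2.4, and change from baseline in the two admission counts does not measure change in resource use

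*SAP*

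**What the plan says.** SAP 5.2.2 lists "The CBL to Week 78 in RUD Lite" and "The CBL to Week 52 in QoL-AD (subject and informant) and RUD Lite scores" among the additional secondary efficacy endpoints. SAP 2.2 places RUD Lite under the other secondary clinical objectives. SAP 8.3.3 uses the primary-endpoint MMRM to "evaluate the between-treatment difference for the key secondary endpoints and the other secondary endpoints using the FAS", with p-values and confidence intervals, and makes no exception for RUD Lite. Protocol 10.7.3 had left the method for these endpoints (MMRM, ANCOVA or nonparametric) to the SAP.

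SAP 8.2.4 gives a total-score rule for every other efficacy scale but none for RUD Lite. Its items "will be listed and summarized by treatment and by baseline MMSE using descriptive statistics", and "Missing data will be left blank without imputation". The four caregiver items look back over a fixed 30 days. The two admission items do not: "Number of times the subject is admitted in a hospital (for more than 24 hours) since last visit" and "Number of times the subject is admitted in a hospital emergency room (for less than 24 hours) since last visit".

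The Schedule of Assessments (Protocol Appendix 2, SAP Appendix 1) has RUD Lite at Baseline, Week 52, Week 78 and early termination (ET) only. The retrieved-dropout visit list in Protocol 7.2.15 does not include it. SAP 8.3.1 assigns early-discontinuation records to analysis visits by study day and applies the same algorithm to the other efficacy endpoints. SAP Table 7 gives days 2 to 456 for Week 52 and days 457 to 592 for Week 78.

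**The concern.** There are two problems. First, the endpoint section speaks of change in a score and the analysis section sends it to a model that needs one numeric outcome, but the scoring section supplies no score and plans descriptive item summaries. A programmer cannot follow all three sections.

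Second, a change from baseline compares like with like only if both values cover the same length of time. The 30-day items meet that condition. The admission counts do not clearly meet it under either meaning of the last visit. Reported change in admissions could then reflect how far back the respondent was asked to look, or could describe only a minority of the treatment period, while being read as change in healthcare use.

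**Working it through.** The documents give no power, rate or variance for RUD Lite, so there is no plan figure to reproduce. The check has three steps.

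**1. Recall lengths.** Scheduled days are from the Schedule of Assessments: Week 39 = day 274, Week 52 = day 365, Week 65 = day 456, Week 78 = day 547. Week = (day − 1)/7. Visit windows of ±14 days are ignored.

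| | Last RUD Lite assessment | Last clinic visit |
|---|---|---|
| Baseline | undefined (no earlier RUD Lite) | time since the last screening visit, at most 13 weeks |
| Week 52 | 52 − 0 = 52 weeks | 52 − 39 = 13 weeks |
| Week 78 | 78 − 52 = 26 weeks | 78 − 65 = 13 weeks |
| Follow-up covered by both scheduled records | (52 + 26)/78 = 100% | (13 + 13)/78 = 33% |
| Covered by the Week 78 record alone | 26/78 = 33% | 13/78 = 17% |

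On the clinic-visit reading, baseline recall is not fixed. Screening Part 1 may be up to 13 weeks before baseline (Protocol 7.2.1), Part 2 has no window of its own, and either may be the last visit.

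**2. Change from baseline when nothing changes.** With a constant rate of r admissions per year, expected change = r × (recall at visit − recall at baseline)/52. Assumptions, because the documents give no values: r from 0.1 to 0.5, and baseline recall from 0 to 13 weeks.

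Last RUD Lite assessment:
- Week 52: lowest 0.1 × (52 − 13)/52 = +0.075; highest 0.5 × (52 − 0)/52 = +0.50
- Week 78: lowest 0.1 × (26 − 13)/52 = +0.025; highest 0.5 × (26 − 0)/52 = +0.25
- At r = 0.3 and baseline recall 0: +0.30 at Week 52 and +0.15 at Week 78, an apparent halving between visits produced by recall alone

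Last clinic visit, either visit:
- lowest r × (13 − 13)/52 = 0; highest 0.5 × (13 − 0)/52 = +0.125

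**3. ET records.** On the last-RUD reading, an ET record at week 4 has 4 weeks of recall and a scheduled Week 52 record has 52. Table 7 maps both to Week 52, although recall differs by a factor of 52/4 = 13. On the clinic-visit reading, ET recall is bounded by the spacing of clinic visits, about 13 weeks.

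**The case against.** The strongest reply is that the only rule specific to RUD Lite is the descriptive one in SAP 8.2.4, and a specific rule normally limits a general one. If so, no score is needed and no p-value arises. That may well be the intent. It means a reader should not infer from 8.3.3 that the MMRM is settled for RUD Lite: the documents support a conflict, not a confirmed modelling error. But the change-from-baseline endpoint in 5.2.2 remains, and so does the recall problem.

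Second, 8.3.3 targets the difference between arms, and at a scheduled visit both arms have the same recall length. This stands. A reader might infer that the treatment comparison is biased; the documents do not support that for on-schedule records. A bias could enter through ET records if dropout timing differs by arm, mainly on the last-RUD reading, but nothing in the documents shows that it will.

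Third, sampling part of follow-up is not a flaw in itself. Two 30-day windows cover 60 of 546 days (11%), and change from baseline is accepted for those items. This also stands: the 33% coverage calls for labelling, whereas unequal or undefined recall is what invalidates the change.

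Fourth, hospital admissions outside the recall periods are not lost to the trial. Inpatient hospitalization is an SAE criterion (Protocol 8.1.2), and AEs are collected from consent to the Safety Follow-up Visit (8.4.1). This stands for inpatient stays. Protocol 8.1.2 generally excepts emergency-room visits without admission and preplanned or elective procedures, so SAE records cannot replace the emergency-room item.

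Finally, the RUD Lite form and eCRF may fix the recall wording, including a separate baseline period. They are not among the documents, and the SAP should state the answer.

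**Conclusion.** The point holds in a limited form. SAP 5.2.2 and 8.3.3 cannot both be followed together with 8.2.4 and must be reconciled. Change from baseline in the two admission counts does not measure change in resource use, because baseline recall is undefined or variable and, on the last-RUD reading, recall also differs between Weeks 52 and 78.

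The ranges in the second step are illustrations. They rest on assumed rates, assumed baseline recall and a constant rate. It would be tempting to fix baseline recall at 13 weeks from screening on the last-RUD reading, but no RUD Lite is done at screening, so no single value can be defended.

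The artefact affects within-arm change, comparison between visits, and ET records pooled with Week 52. On-schedule comparisons between arms share the same recall, and the 30-day caregiver items are sound. RUD Lite lies outside the controlled tests and additional endpoints carry nominal p-values (SAP 8.1.5), so primary and key secondary conclusions are untouched. This is a minor but easily corrected defect.

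**What to change.** In SAP 5.2.2 and 8.3.3, limit RUD Lite change from baseline to the items with the fixed 30-day recall, and state that RUD Lite is analysed by item under 8.2.4.

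Report the two admission items by arm as events per person-time of recall, or with a count model using log recall time as offset, without change from baseline. This handles the unequal scheduled periods and gives each ET record its own recall time.

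Define the last visit in 8.2.4. If it is the clinic visit, label the admission items with the weeks covered and take total inpatient hospitalizations from the SAE records, noting their exceptions for emergency-room visits without admission and for preplanned or elective procedures.

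The cost is SAP wording and a change to one table, best made before unblinding. The downside is that the admission items lose their change-from-baseline format.
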